6.4.1 Inclusion Criteria

- 1) Couples with \leq two failed fresh IVF/ICSI embryo transfer cycles.
- 2) Age \geq 18 and \leq 40 years.
- 3) BMI: $18-30 \text{ kg/m}^2$.
- 4) Normal uterine cavity under ultrasound.
- 5) Subject and her husband/partner must have read and signed the Informed

Protocol Version: 3.0 / Jan 31, 2018 20 / 49

trial

Consents form.

6) At least four normally fertilized oocytes (2PN) in the current cycle.

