6.4.2 Exclusion Criteria

- 1) Male with non-ejaculated sperm.
- 2) Subjects with abnormal, undiagnosed gynecological bleeding or with genitourinary malformations.
- 3) Subjects with any contraindication to COS for ART or to gonadotropins.
- 4) Planned "freeze all" cycle (oocytes or embryos).
- 5) Planned PGS or PGD cycle.
- 6) Concurrent participation in another clinical study.

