- If the EEVA result shows "NR" (No Result) or there are only poor-quality embryos, the embryologist will grade the embryos with morphology (Alpha Scientists in Reproductive Medicine and ESHRE Special Interest Group Embryology, 2011) and apply the decision grid used in the control group.
- If two or more embryos have the same EEVA score, preference should be given to the embryos with better morphology and subject to the embryologist's decision grid used in the control group.
- National/regional regulations and procedures will be followed to manage the remaining embryos, provided that in each case the provisions of the Germany Embryo Protection Act are observed.

In the control treatment arm:

- On Day 1 of embryo culture, all 2PN zygotes are transferred by embryologists into the GERI dishes which have been pre-equilibrated with embryo culture medium routinely used in their laboratory. The GERI dishes are then placed in a conventional incubator for culture until Day 3. Gas with 6% CO₂ (or whichever CO₂ concentration is required to meet manufacturers requirements for optimal pH of their culture media) and 5% O₂ is recommended. If a different gas composition is used, this must be the same for both test and control arms.
- On Day 2 of embryo culture, the embryos may or may not be taken out of the incubators for observation using bench-top microscopy, to follow the routine protocols of the laboratory.

Protocol Version: 3.0 / Jan 31, 2018 23 / 49

trial

• On Day 3 of embryo culture, all embryos are assessed using a bench-top microscope by embryologists, at a recommended time of 68±1 hours post insemination. (Alpha Scientists in Reproductive Medicine and ESHRE Special Interest Group Embryology, 2011). The embryo(s) with optimal cell stage and grade will be transferred. National/regional regulations and procedures will be followed to manage the remaining embryos, provided that in each case the provisions of the Germany Embryo Protection Act are observed.

Please be advised that there is no restriction on the number of embryos to be transferred but we recommend a single embryo transfer in this study.

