# **8** Protocol Deviations and Analysis Sets

#### 8.1 Definition of Protocol Deviations

The definition of the major and minor protocol deviations are as follows.

Major protocol deviations are:

- 1. The number of 2PNs is less than 4 or missing
- 2. Subject is not randomized or not treated as randomized
- 3. Technical issues with GERI which are not reported as device deficiency
- 4. EEVA test applied to Poor Quality embryos instead of standard morphology
- 5. Control arm- Embryos with optimal cell number and grade were NOT transferred

All other deviations will be counted as minor deviations.

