#### Per Protocol (PP) dataset:

(PP) dataset is defined as:

Subjects, who completed the study without major protocol deviation, and:

- For subject randomized Geri+ group:
  - o embryos are cultured to Day 3, and are assessed by Eeva per Eeva IFU, or by standard morphology if this subject only has poor quality embryos;
  - embryo(s) with the highest Eeva score (for subjects with good and fair quality embryos), or best morphology grade (for subjects with poor quality embryos only, or with poor quality embryos and no more than one good/fair quality embryos) is/are transferred on Day 3 of embryo culture;
- For subjected randomized to Control group:
  - Embryos are cultured to Day 3, and the embryo(s) with the optimal cell number and grade is/are transferred.

Major protocol deviations are defined in section 8.1

The FA population is the primary analysis population.

PP population is used for sensitivity analysis. PP population will be considered only if it is less than 90% of FA population and more than 40% of total planned number of subjects.

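### SAP 8.2 can leave GERI+ women with no EEVA result outside the per-protocol set although they were handled as protocol 6.8 directs

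*SAP*

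**What the plan says.** Protocol 6.8, experimental arm, provides for the case where EEVA gives no usable ranking. Its instruction for an NR output continues "No Result) or there are only poor-quality embryos, the embryologist will grade the embryos with morphology", after which the control group's decision grid applies. NR and poor-only are two separate triggers.

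SAP 8.2 defines PP membership as completion without a major deviation, plus conditions by arm. For GERI+ there are two bullets:

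- **Assessment:** Eeva according to its IFU, "or by standard morphology if this subject only has poor quality embryos".
- **Transfer:** "embryo(s) with the highest Eeva score (for subjects with good and fair quality embryos". The best morphology grade is accepted instead for women with poor embryos only, or "with poor quality embryos and no more than one good/fair quality embryos".

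Neither bullet mentions NR. The control-arm condition asks for culture to Day 3 and transfer by cell number and grade, so it contains nothing that depends on an EEVA output.

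SAP 8.2 makes the full analysis (FA) set primary and PP the sensitivity set. PP is considered only if it is below 90% of FA and above 40% of the planned number. SAP 7 reports no change to the planned analyses other than dropping group comparisons, confidence intervals and regression models.

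On deviations, SAP 8.1 lists five major items. The one drawn from the eligibility criteria is "The number of 2PNs is less than 4 or missing". The list closes with "All other deviations will be counted as minor deviations".

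**The concern.** A per-protocol set should keep women who were treated as the protocol instructs. Here the protocol names two reasons to use morphology in the GERI+ arm, and the SAP's membership rule carries over one of them. A woman handled correctly under the other can be removed. Because only GERI+ women can have an NR, the removal is one-sided.

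The set matters somewhat more than its label suggests. Protocol 8.3 names three analysis sets, but SAP 8.2 defines only FA and PP. The sensitivity regression in protocol 8.4.2 has also been dropped by SAP 7. PP is therefore the one remaining check on the FA result. The output that might reveal the affected women, the Eeva conformity table in SAP 13, counts every transfer not based on an Eeva result together and does not separate NR.

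**Working it through.** **Step 1. Set the rules side by side.** Each row is a GERI+ woman. In the first four, protocol 6.8 calls for morphology.

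| Woman | SAP 8.2 assessment bullet | SAP 8.2 transfer bullet |
|---|---|---|
| Poor embryos only | met by morphology | met by morphology |
| NR on all; poor embryos plus one good/fair | met only if the IFU wording covers NR | met by morphology |
| NR on all; poor embryos plus two or more good/fair | met only if the IFU wording covers NR | **not met: no score exists** |
| NR on all; good/fair embryos only | met only if the IFU wording covers NR | **not met: no score exists** |
| Some embryos scored, some NR (if NR is issued per embryo) | met | can be met: a highest score exists |

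The gap at the transfer step is confined to rows three and four.

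**Step 2. Reproduce the plan's figures used for scale.** Protocol 8.1 gives 30% in controls and a 25% relative increase, so 0.30 × 1.25 = 37.5% for GERI+. The mean of the two rates is 0.3375. With two-sided alpha 0.05 and 80% power:

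n = [1.960 × √(2 × 0.3375 × 0.6625) + 0.842 × √(0.30 × 0.70 + 0.375 × 0.625)]² / 0.075² = 622.8, so 623 per group.

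623 / 0.9 = 692.2, so 693 per group and 1,386 in total. Both match the protocol.

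**Step 3. Size of the PP gate.** If all 1,386 women are in FA, 0.90 × 1,386 = 1,247.4 and 0.40 × 1,386 = 554.4. PP is then considered only with 555 to 1,247 women, that is, after at least 1,386 − 1,247 = 139 exclusions for any reason.

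**Step 4. Effect of wrongly dropped women on the GERI+ PP rate.** If k women with pregnancy rate q are dropped from n women with rate p, the shift is k(p − q)/(n − k). Two arm sizes are assumed: 623 (planned evaluable number) and 278 (about half of 555).

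| n | Start | Drop one pregnant | Drop one not pregnant | Needed for a 1-point shift |
|---|---|---|---|---|
| 623 | 234/623 = 37.56% | 233/622 = 37.46% (−0.10) | 234/622 = 37.62% (+0.06) | 10 all pregnant, or 17 all not |
| 278 | 104/278 = 37.41% | 103/277 = 37.18% (−0.23) | 104/277 = 37.55% (+0.14) | 5 all pregnant, or 8 all not |

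If the dropped women conceive at the arm's rate, p − q is zero and so is the shift. For example, dropping 8 women of whom 3 are pregnant gives 231/615 = 37.56%, unchanged from 234/623.

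**Step 5. Number of women.** The documents give no NR rate. If 1% to 20% of the 693 GERI+ women fell into rows three and four (an assumption), 7 to 139 would leave PP, or 0.5% to 10% of FA.

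**The case against.** **The IFU may deal with NR.** The assessment bullet refers to the Eeva IFU, which is not among the documents, and it may treat an NR as a proper Eeva assessment. That stands for the assessment step. It does not help at the transfer step, where a woman in rows three or four still needs a score she does not have.

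**The SAP is silent rather than exclusionary.** Nobody wrote that NR women are to be removed, and a programmer might keep them. This is fair, and it is why the point is put as a literal reading. A membership rule should not depend on that choice.

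**The effect is small.** This stands. FA is primary, no comparisons or confidence intervals are planned, SAP 10.2.2 tabulates and lists PP exclusion reasons by arm, and PP may not be used at all if it reaches 90% of FA.

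**A stronger reading about eligibility.** A reader might infer that SAP 8.1 departs from the protocol because, of the six inclusion and six exclusion criteria in protocol 6.4, only the 2PN count ("At least four normally fertilized oocytes (2PN) in the current cycle") is listed as major. The documents do not support this:

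- Protocol 8.3 leaves major violations undefined beyond factors likely to affect efficacy. Specifying them is a proper task for a SAP and need not be declared as a change.
- Several criteria, such as "Concurrent participation in another clinical study", are not plainly factors of that kind. Others are caught elsewhere: a freeze-all woman without a Day 3 transfer fails PP anyway.
- Age is the one criterion that the protocol itself treats as prognostic, as a stratification factor (6.7, 8.2) and a named confounder (6.11). Even so, few breaches are likely. The two randomization strata together span exactly 18 to 40, screening ends before randomization (7.3), and SAP 10.1 counts screen failures, enrolled and randomized women separately. The documents do not say that the randomization system blocks a woman outside the limits.

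**Conclusion.** The mismatch between protocol 6.8 and SAP 8.2 is real, undeclared and confined to the GERI+ arm. It concerns women with no EEVA result on any embryo who have two or more good or fair embryos, or good or fair embryos only. Severity is minor.

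The documents give neither the number affected nor the direction of any shift in the PP rate. A reader might infer that the rule biases the PP result. That would require the dropped women to conceive at a different rate from the rest of the arm, and nothing in the documents shows this. The per-woman figures are for scale only and rest on the planned 37.5% rate and the assumed arm sizes.

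The classification of an age breach as minor is not an error. It supports a suggestion only.

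**What to change.** 1. Amend both GERI+ bullets in SAP 8.2 so that PP accepts women with an EEVA NR who were graded and transferred by morphology as protocol 6.8 instructs. Changing only one bullet would leave the other in the way.
2. Record the clarification in SAP 7.
3. Optional: list a breach of the age criterion as major in SAP 8.1 for both arms. First state whether the limit of 40 means completed years. SAP 11.1 derives a decimal age from the consent date of the subject or partner, with rules for missing days and months. Used directly, it would flag a woman aged 40.5.

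The cost is a few lines of SAP text and re-derivation of one PP flag. No sample size, power or alpha figure changes. NR women can be sought in the GERI+ Day 3 assessment listing (SAP 14.3.5). The form itself is not in the documents, so a manual check of that listing may be needed.

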8.3 Analysis Sets

Three analysis sets will be used: the Full Analysis dataset, the Per Protocol dataset and the Subgroup Analysis dataset.

- Full Analysis (FA-) dataset includes all randomized subjects. Subjects will be presented as randomized.
- Per Protocol (PP) dataset includes all subjects who have been treated according to the Clinical Trial Protocol and have received Day 3 fresh embryo transfer, with no major Clinical Trial Protocol violation in respect of factors likely to affect the efficacy of treatment.
- · Subgroup Analysis dataset (SA):Subjects who had embryos transferred which were either good or fair (i.e. not poor quality)

32 / 49

trial

• .

The FA population is the primary analysis population. PP population is used for sensitivity analysis. SA population is used for supportive analysis.

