# **5** Objectives and Endpoints

	Objective	Endpoint	IAP section
Trial Objective	The main aim of this trial is to evaluate the overall clinical value of GERI+ as an integrated embryo culture and assessment system, providing an undisturbed culture environment, continuous monitoring of embryo development and automated scoring using a predictive algorithm	Primary Endpoint Clinical pregnancy with positive fetal heart beat in gestational week 6-8 after fresh embryo transfer on Day 3.	14.1
		Secondary Endpoints  1. Number of utilizable embryos  2. Number of good quality embryos  3. Number of non-viable embryos  4. Implantation with positive fetal heart beat  5. Biochemical pregnancy  6. Ongoing pregnancy  7. Multiple pregnancy  8. Ectopic pregnancy  9. Spontaneous miscarriage	14.2

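### SAP 8.2 ties per-protocol membership to a Day 3 transfer in the GERI+ arm but names no transfer day for controls, so women transferred after Day 3 may be handled differently by arm

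*SAP*

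**What the plan says.** Protocol 8.3 defines one PP rule for both arms. Subjects must have been "treated according to the Clinical Trial Protocol and have received Day 3 fresh embryo transfer", with no major violation likely to affect efficacy.

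SAP 8.2 replaces this with a common condition and a bullet list for each arm:

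- **Both arms:** "Subjects, who completed the study without major protocol deviation, and" the arm-specific conditions.
- **GERI+:** embryos are cultured to Day 3 and assessed as specified. As a further condition, the selected embryo(s) "is/are transferred on Day 3 of embryo culture".
- **Control:** "Embryos are cultured to Day 3, and the embryo(s) with the optimal cell number and grade is/are transferred".

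SAP 8.1 lists five major deviations. The one specific to controls reads "Control arm- Embryos with optimal cell number and grade were NOT transferred". None of the five mentions the day of transfer, and the section closes with "All other deviations will be counted as minor deviations".

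The primary endpoint in SAP 5 makes no distinction by arm: "Clinical pregnancy with positive fetal heart beat in gestational week 6-8 after fresh embryo transfer on Day 3".

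SAP 7 says that the protocol's methods were adopted without change, except that between-group comparisons, confidence intervals and regression models are dropped. It does not mention the PP definition.

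**The concern.** A per-protocol set is useful only if the same rule decides membership in both arms. Here a post-randomisation event, transfer after Day 3, excludes a woman in one arm and, on the literal text, does not exclude her in the other. Women whose transfer is postponed need not have the same prognosis as those transferred on Day 3. Removing them from one arm only would make the two PP rates describe differently selected groups.

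The set also matters somewhat more than usual in this plan. The logistic regression that Protocol 8.4.2 offered as a sensitivity analysis is dropped in SAP 7, and the Subgroup Analysis set of Protocol 8.3 does not appear in SAP 8.2. PP is therefore the remaining sensitivity view of the primary endpoint. It is also the only set meant to enforce the Day 3 question, because the rate in SAP 14.1 is taken over all women with a transfer attempted. The planned transfer table in SAP 14.3.6 does not show transfer day, so a reader of the tables could not see how many women were affected.

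**Working it through.** **Step 1: the literal rule, case by case.** The inputs are SAP 8.1, 8.2 and 10.1.

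| Case | GERI+ arm | Control arm |
|---|---|---|
| Transfer before Day 3 | Out: not cultured to Day 3 | Out: not cultured to Day 3 |
| Fresh transfer on Day 3, other conditions met | In | In |
| Fresh transfer cancelled | Out: SAP 10.1 lists this under not completing the study | Out: same reason |
| Transfer after Day 3, best embryo chosen | Out: fails the Day 3 transfer condition | In: no transfer-day condition, and the deviation is minor under SAP 8.1 |

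Only the last row differs by arm. Protocol 8.3 would put that row out in both arms.

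**Step 2: the plan's own figures.** Protocol 8.1 assumes 30% in controls and a 25% relative increase, so 0.30 x 1.25 = 37.5%, a planned difference of 7.5 points. The sample size uses

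n = [1.960 x sqrt(2 x 0.3375 x 0.6625) + 0.842 x sqrt(0.30 x 0.70 + 0.375 x 0.625)]^2 / 0.075^2

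This gives 623 per group after rounding up. With 10% drop-out, 623 / 0.90 = 692.2, rounded up to 693 per group and 1,386 in total. The plan's figures reproduce, and this point does not dispute them.

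**Step 3: when PP is used.** SAP 8.2 considers PP only if it is below 90% of FA and above 40% of the planned number. The lower limit is 0.40 x 1,386 = 554.4 subjects. If all 1,386 are randomised, the upper limit is 0.90 x 1,386 = 1,247.4.

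**Step 4: illustration of size.** The documents give neither the share of transfers after Day 3 nor the pregnancy rate in those women, so both are assumed. Let s be the share of the control PP set transferred after Day 3, r their pregnancy rate, and 30% the rate in controls transferred on Day 3. Then

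control PP rate = (1 - s) x 30% + s x r, so shift = s x (r - 30%)

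| s (assumed) | r = 15% | r = 45% |
|---|---|---|
| 2% | 0.02 x (-15) = -0.30 points | 0.02 x 15 = +0.30 points |
| 5% | 0.05 x (-15) = -0.75 points | 0.05 x 15 = +0.75 points |
| 10% | 0.10 x (-15) = -1.50 points | 0.10 x 15 = +1.50 points |

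At s = 5% the shift is 0.75 / 7.5 = 10% of the planned difference, in either direction. If the same 5% applied in the GERI+ arm, about 0.05 x 693 = 35 women would leave PP there for a reason that removes no controls. As s falls to zero, so does the shift.

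**The case against.** The best defence is that culture to Day 3 followed by transfer naturally means transfer on Day 3. Protocol 6.8 describes control culture until Day 3 and assessment on that day, and both Protocol 8.3 and the endpoint point the same way. On that view the control bullet is loosely drafted and a later transfer does not satisfy it. This is plausible as intent, and it is why confidence is only medium. The wording does not secure it, because the GERI+ bullets state culture to Day 3 and transfer on Day 3 as two separate conditions and only the first is carried over to controls. The control-specific major deviation might catch some later transfers if a different embryo was then chosen, but it concerns which embryo was transferred, not when.

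A reader might also infer more than the documents support:

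- **That any off-schedule transfer is affected.** A transfer before Day 3 fails PP in both arms.
- **That the missing word fresh is a second asymmetry.** It is missing from both arms' bullets, and a cancelled fresh transfer already counts as not completing the study.
- **That SAP 7 declares no change at all.** It does declare that comparisons, confidence intervals and models are dropped. It is silent on the PP definition.
- **That unblinded staff will use the transfer day selectively.** Protocol 6.6 says that staff are not blinded. No section gives them discretion over transfer day or describes a later-transfer option. SAP 14.3.3 tabulates blastocyst media, which makes later culture conceivable but does not show that it happens.
- **That the result is biased towards one arm.** Nothing in the documents fixes the sign.

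**Conclusion.** The point holds in limited form. Read literally, SAP 8.2 treats transfers after Day 3 differently by arm, conflicts with Protocol 8.3, and does so without declaration in SAP 7. It may be no more than a drafting slip, but the text should not leave that to the programmer.

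The consequence is small. PP is a sensitivity set, summarised by percentages with no test or interval, and used only within its size limits. The FA analysis, which is primary, is unaffected. The illustrated 0.75 points rests wholly on assumed values (5% transferred later, with a rate of 45% or 15% against 30%). The true size and direction cannot be derived from the documents. Severity is minor and confidence medium.

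**What to change.** Reconcile the control bullet in SAP 8.2 with the GERI+ bullet and with Protocol 8.3, so that both arms carry the same Day 3 fresh-transfer condition for PP. List the absence of a Day 3 fresh transfer among the PP exclusion reasons in SAP 10.2.2 for both arms. Add transfer day by arm to the table in SAP 14.3.6, so that readers can see how many women the rule affects. Women transferred on another day stay in FA as randomised.

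This concerns membership of an analysis set only and says nothing about when a transfer should be done. The cost is SAP wording and one extra table row, since Protocol 7.3 already collects the date and time of transfer in the eCRF. The downside is that the control PP set may become slightly smaller. The sample size of 1,386 does not change.

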#### 9 General Specifications for Data Analyses

All analyses will be performed for the two treatment groups.

Descriptive statistics such as

- Number of subjects (n), number of subjects with missing values (Missing),
- mean, standard deviation (SD),
- median, first quartile (Q1), third quartile (Q3),
- minimum and maximum

will be provided for all continuous variables.

Mean, median, Q1 and Q3 will have one decimal place more than the raw data and SD will have 2 decimal places more than the raw data. The decimal place for minimum and maximum values will be same as the raw data.

The frequency (n) and percentage will be calculated for all categorical variables including missing observations and the percentages will be rounded off to one decimal place.

Unless otherwise stated the calculation of proportions will be based on the number of subjects of the analysis set of interest. Therefore counts of missing observations will be included in the denominator and presented as a separate category.

In case the analysis refers only to certain visits percentages will be based on the number of subjects still present in the trial at that visit, unless otherwise specified.

All the tables will provide for the two treatment groups (GERI+ incubator and Conventional incubator) and overall.

